The primary efficacy variable is time to alleviation of COVID-19-related symptoms of cough, dyspnea, chills, feeling feverish, repeated shaking with chills, muscle pain, headache, sore throat, and new loss of taste or smell, defined as symptom-free for a continuous period of \geq 24 hours (ie, \geq 3 AM/PM assessments) by day 30. The primary analysis will be based on the intent-to-treat population (all randomized patients). To increase precision of treatment effect estimation and inference, a Cox proportional hazards model will be used to allow for inclusion of additional prespecified prognostic baseline covariates. The median time to event and 95% confidence intervals will be summarized by treatment arm, and Kaplan-Meier estimates of the survival curves will also be generated. The secondary efficacy endpoints of percentage of patients with hospital admission or death by day 30; all-cause mortality by day 30; COVID-19-related mortality by day 30; percentage of patients with subsequent emergency department visit or hospital admission for reasons attributable to COVID-19 by day 30; and percentage of patients with alleviation of COVID-19-related symptoms of cough, dyspnea, chills, feeling feverish, repeated shaking with chills, muscle pain, headache, sore throat, and new loss of taste or smell, defined as symptom-free for a continuous period of ≥ 24 hours (ie, ≥ 3 AM/PM assessments) by day 7, by day 14, and by day 30 will be analyzed using a logistic regression model. This will improve the precision of treatment effect estimation and inference by allowing for baseline covariate adjustments to be included in the model. Analysis of the secondary efficacy endpoint of time to hospital admission or death will be performed using the same method as that used for the primary efficacy endpoint. The secondary efficacy endpoint of change from baseline in oxygen saturation levels will be summarized descriptively at all timepoints captured in the eDiary. The secondary efficacy endpoint of change from baseline in COVID-19 viral load in nasopharyngeal sample at day 30 will be summarized descriptively.

Safety

The safety population will include all randomized patients who receive at least 1 dose of double-blind study medication. Safety will be evaluated by summarizing the incidence of adverse events. Comparative analyses will be done on adverse events of special interest (eg, oral candidiasis).

Interim Safety Review

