4.3.2 Key Secondary Endpoint Estimand

The attributes of the estimand for the key secondary endpoint included in the multiplicity control procedure of this trial are:

- 1. Treatment regimens: ciclesonide and placebo
- 2. Populations of interest: patients meeting inclusion/exclusion criteria grouped according to randomized treatment assignment reflect the target population
- 3. Patient-level outcome: binary indicator of alleviation of COVID-19-related symptoms of cough, dyspnea, chills, feeling feverish, repeated shaking with chills, muscle pain, headache, sore throat, and new loss of taste or smell, defined as symptom-free for a continuous period of \geq 24 hours (ie, \geq 3 AM/PM assessments) by day 14
- 4. Intercurrent events: regardless of the use of rescue medications, protocol violations, or investigational product discontinuation
- 5. Population-level summary measure: difference in response probabilities between treatment regimens

The **treatment-policy strategy** for this estimand is the difference in probabilities of alleviation of COVID-19-related symptoms of cough, dyspnea, chills, feeling feverish, repeated shaking with chills, muscle pain, headache, sore throat, and new loss of taste or smell, defined as symptom-free for a continuous period of ≥ 24 hours (ie, ≥ 3 AM/PM assessments) by day 14 between those assigned to ciclesonide and those assigned to placebo, regardless of patient's use of rescue medications, protocol violations, or investigational product discontinuation. Therefore, for all patients in the ITT analysis set, all observed on-study data will be analyzed in accordance with the definition set forth above for intercurrent events.

Since death and hospitalization are not part of this key secondary endpoint patient level-outcome definition, a composite strategy will be used to handle these situations. If a patient dies or is hospitalized, then the value attributed in that scenario would be failure to achieve alleviation of COVID-19-related symptoms which ascribes the most unfavorable value.

Estimands for other secondary efficacy endpoints included in the multiplicity control procedure (section 10.7.3) will be described in the Statistical Analysis Plan (SAP).

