| HCP to contact patient for health status check, to collect adverse event and concomitant medication information, and to confirm/clarify information recorded in eDiary ^e | | X (days 2, 4, 6, 8, 10, 12, 14, 21 ± 2 days, and 30 ± 2 days) | | |
| Return of eDiary and investigational product (ie, used and unused MDIs) | | X (day 30 [window of $+ 2 \text{ days}])^d$ | | Х |
| HCP to contact patient to collect follow-up safety and outcome data | | | X (day 37 ± 4 days and day 60 ± 7 days) | \mathbf{X}^{f} |
| AM = morning (prior to noon); BID = twice a day; COVID-19 = coronavirus disease 2019; eDiary = electronic diary; HCP = healthcare provider; IP = investigational | | | | |

product; MDI = metered-dose inhaler; PM = evening (prior to midnight); SARS-CoV-2 = Severe Acute Respiratory Syndrome Coronavirus 2.

- a^{a} = To include date of onset of COVID-19 symptoms.
- = To meet criteria for inclusion, patient must have a positive SARS-CoV-2 molecular or antigen diagnostic test within 72 hours prior to enrollment.
- ^c = Note on day 1 dosing: In the event the patient receives the initial dose of IP at or before noon during the screening/enrollment/randomization visit, this will be considered to be the day 1 AM dose and the patient will be instructed to perform symptom assessments and oxygen saturation level monitoring, and to self-administer the day 1 PM dose prior to midnight. In the event the patient receives the initial dose of IP any time after noon during the screening/enrollment/randomization visit, this will be considered to be the day 1 PM dose and the patient will be instructed to wait until morning to perform symptom assessments, oxygen saturation level monitoring, and to self-administer the next dose (ie, day 2 AM dose). Note on day 30 dosing: Patients will be instructed to continue dosing through day 30. In the event the patient has their day 30 (window of + 2 days) visit on day 30, they will be instructed to perform symptom assessments and oxygen saturation level monitoring, and to self-administer the day 30 doses as per their typical schedule/routine. Thus, depending upon the time of day that the day 30 visit occurs, patients may or may not receive both doses on day 30. For patients that have their day 30 visit on day 31 or day 32, they will be instructed to complete through the day 30 PM dose and then discontinue investigational product dosing, symptom assessments, and oxygen saturation level monitoring.

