5.3.1 Screening/Enrollment/Randomization Visit

Before any study-specific activities/procedures, the appropriate written informed consent must be obtained (see section 12.2).

The following procedures will be conducted prior to administration of investigational product (ie, predose):

- Review inclusion/exclusion criteria.
- Confirm positive SARS-CoV-2 molecular or antigen diagnostic test (Note: patient must have a positive SARS-CoV-2 molecular or antigen diagnostic test within 72 hours prior to enrollment).
- Review demographics, medical history, and medication history (including prior [within 90 days before screening/enrollment/randomization visit] and current medications). Date of onset of COVID-19 symptoms should be recorded.
- Perform full physical examination, including measurements of vital signs (blood pressure [mm Hg], respiratory rate [breaths per minute], temperature [°F], and heart rate [beats per minute]), oxygen saturation level, height, weight, and calculation of body mass index.
- Perform urine pregnancy test for females of childbearing potential within 48 hours prior to enrollment.
- Collect nasopharyngeal sample for COVID-19 viral load analysis.
- Provide patient with the eDiary and instruct on usage.
- Provide patient with pulse oximeter and instruct on usage. Instruct patient to seek medical attention immediately should oxygen saturation levels fall to 93% or below.
- Instruct patient on recording severity of COVID-19-related symptoms of cough, dyspnea, chills, and feeling feverish using a 4-point scale where 0 = absent, 1 = mild, 2 = moderate, and 3 = severe, and have patient record baseline results in the eDiary.
- Instruct patient on recording presence/absence of COVID-19-related symptoms of repeated shaking with chills, muscle pain, headache, sore throat, and new loss of taste or smell, and have patient record baseline results in the eDiary.
- Provide patient with study personnel contact information and instruct patient (or their representative) to notify study personnel directly in the event they visit an emergency department or are hospitalized during their participation in the study.
- Dispense investigational product according to treatment assignment.

• Train patient on appropriate MDI inhalation technique and instruct patient to rinse their mouth with water following inhalation of investigational product.

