6 PATIENT ELIGIBILITY AND WITHDRAWAL CRITERIA

6.1 Number of Patients

Approximately 400 patients (200 in each arm) will be randomized. A sample size justification is provided in section 10.1.

It is anticipated that patients will be enrolled at up to 15 study sites in the United States.

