10.1 Sample Size and Power

This study is designed to assess the efficacy and safety of ciclesonide MDI plus standard supportive care compared with placebo MDI plus standard supportive care. The primary endpoint is time to alleviation of COVID-19-related symptoms of cough, dyspnea, chills, feeling feverish, repeated shaking with chills, muscle pain, headache, sore throat, and new loss of taste or smell, defined as symptom-free for a continuous period of ≥ 24 hours (ie, ≥ 3 AM/PM assessments) by day 30. The Cox proportional hazards model will be used to compare treatment arms with respect to time to alleviation (or recovery) of COVID-19-related symptoms as defined in the primary endpoint. Total number of events (recoveries) as well as the expected rate of recovery (or hazard ratio) for treatment compared to placebo are key determinants of power. The expected median survival time is approximately 7 days for the ciclesonide arm and approximately 11 days for the placebo arm (hazard ratio of approximately 1.58) with a total study duration of 30 days. For 90% power, approximately 201 events (recoveries) are required to detect this anticipated increase in rate of recovery between ciclesonide and placebo. A sample size of 232 patients (116 per arm) is required to achieve the specified 90% power at an $\alpha = 0.05$ for this study. To account for an unknown drop-out rate in this patient population as well as other factors that may impact the overall power of the study, the planned sample size was increased to 400 patients (200 in each arm) for this study. Note that these are best estimates at this point as there is still much uncertainty regarding COVID-19.

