10.4 Demographic and Baseline Characteristics

Demographics and baseline characteristics, medical history, baseline physical examination findings, baseline vital sign data, baseline height, baseline weight, and baseline body mass index will be summarized descriptively by treatment group.

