10.7 Analysis of Efficacy Data

10.7.1 Primary Efficacy Endpoint

The primary efficacy variable is time to alleviation of COVID-19-related symptoms of cough, dyspnea, chills, feeling feverish, repeated shaking with chills, muscle pain, headache, sore throat, and new loss of taste or smell, defined as symptom-free for a continuous period of \geq 24 hours (ie, \geq 3 AM/PM assessments) by day 30. The primary analysis will be based on the ITT population (all randomized patients). To improve the precision of treatment effect estimation and inference, baseline covariate adjustments will be made for gender, age, race, and body mass index, as these are known COVID-19 risk factors. A Cox proportional hazards model will be used to allow for inclusion of these additional covariates. The median time to event and 95% confidence intervals will be summarized by treatment arm, and Kaplan-Meier estimates of the survival curves will also be generated.

The SAP will describe how missing data will be handled in the primary analysis. In addition, a sensitivity analysis for the primary endpoint will be conducted using a tipping point analysis that will systematically and comprehensively vary assumptions about the missing outcomes on the treatment arms. Details will be provided in the SAP.

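### The primary Cox model and the alleviation logistic models omit baseline symptom burden and days since onset, both already collected; the tests are valid but some efficiency is forgone

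*Combined protocol and SAP*

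**What the plan says.** The synopsis says a Cox model is used "to allow for inclusion of additional prespecified prognostic baseline covariates". Section 10.7.1 then gives the list and the reason for it: "baseline covariate adjustments will be made for gender, age, race, and body mass index, as these are known COVID-19 risk factors". Section 10.7.2 repeats the list for the logistic models, which include alleviation by days 7, 14 and 30, and analyses time to hospital admission or death by the primary method. In both sections the declared aim of adjusting is better precision.

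Two other baseline variables are available. Section 7.1.2 has all nine symptoms assessed predose: four graded 0 to 3 and five as present or absent. Section 5.3.1 states "Date of onset of COVID-19 symptoms should be recorded", and the medical-history footnote to Table 1 in section 5.2 agrees: "To include date of onset of COVID-19 symptoms". Section 10.4 covers "Demographics and baseline characteristics, medical history, baseline physical examination findings" and similar items, but only descriptively. Section 8.2 randomises in kit blocks of 6, with no stratification on either variable.

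The day 14 alleviation estimand in section 4.3.2 is a "difference in response probabilities between treatment regimens". Section 6.1 sets the size: "Approximately 400 patients (200 in each arm) will be randomized". Section 10.1 says of its planning figures that "these are best estimates at this point as there is still much uncertainty regarding COVID-19".

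**The concern.** A covariate improves precision to the extent that it predicts the endpoint being analysed. The four chosen were picked as risk factors for the disease, whereas this endpoint is complete clearance of nine symptoms. Entry (section 6.2) requires only one of fever, cough or dyspnea, with no minimum severity and no limit on symptom duration. Patients can therefore start with very different symptom loads and at different stages of illness. Both features plausibly predict time to clearance better than gender, age, race or body mass index do, although the documents give no figure for this.

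Omitting a prognostic covariate from a Cox model moves the estimated hazard ratio toward 1 relative to the covariate-conditional one, and power falls. The effect also reaches day 14 alleviation, which is second in the fixed testing sequence (section 10.7.3). The odds ratio from that logistic model is, besides, not the difference in probabilities that the estimand asks for.

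**Working it through.** **The plan's own figure.** Inputs from section 10.1: hazard ratio 1.58, α = 0.05 (taken as two-sided), 90% power, medians 7 and 11 days, 30 days of follow-up. Schoenfeld: events = 4(1.960 + 1.282)² / (ln 1.58)² = 42.03 / 0.2092 = 201, as stated. With exponential times the probability of alleviation by day 30 is 1 − exp(−30 ln 2 / 7) = 0.949 and 1 − exp(−30 ln 2 / 11) = 0.849, mean 0.899. So 400 patients give 400 × 0.899 = 360 events without drop-out, and about 99% power at a hazard ratio of 11/7 = 1.571.

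**Assumption.** One standard normal index stands for symptom burden and days since onset together. Its log hazard ratio per SD, beyond the four planned covariates, is 0.15, 0.3, 0.5 or 0.7.

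**Simulation.** N = 400, exponential recovery given the index, placebo median 11 days, censoring at day 30, and drop-out at uniform times where used. There were 5,000 trials per power cell (Monte Carlo SE at most 0.7 points). Hospitalisation and death were not modelled. The scenarios are:

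1. Medians 7 and 11 days hold (conditional hazard ratio 11/7). The model without the index then estimates 1.57, 1.54, 1.48 and 1.43.
2. The planned model itself estimates about 1.59 to 1.60 (conditional 1.625, 1.704, 1.802; strengths 0.3 to 0.7 only).
3. A sensitivity case, not the plan's assumption: the planned model estimates 1.38 to 1.39.

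| Power, % | 0.15 | 0.3 | 0.5 | 0.7 |
|---|---|---|---|---|
| (1) Cox, index omitted | 98.9 | 98.1 | 95.5 | 90.7 |
| (1) Cox, index included | 99.0 | 99.1 | 98.7 | 98.5 |
| (1) Cox, measured index correlated 0.7 with the true one | 98.9 | 98.6 | 97.3 | 95.0 |
| (1) 40% drop-out, omitted | 97.6 | 96.4 | 93.3 | 88.2 |
| (1) 40% drop-out, included | 97.9 | 97.7 | 97.3 | 97.4 |
| (2) Cox, omitted | – | 99.0 | 99.2 | 98.7 |
| (2) 40% drop-out, omitted | – | 98.3 | 98.5 | 98.1 |
| (2) 40% drop-out, included | – | 99.2 | 99.6 | 99.8 |
| (3) Cox, omitted | 85.0 | 86.0 | 85.1 | 84.5 |
| (3) Cox, included | 86.3 | 89.8 | 93.2 | 96.3 |
| (3) Cox, correlation 0.7 | 85.6 | 87.8 | 89.0 | 90.7 |
| (1) Day 14 logistic, omitted | 94.0 | 92.1 | 87.0 | 81.6 |
| (1) Day 14 logistic, included | 94.2 | 93.3 | 90.1 | 88.6 |

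In (2) without drop-out, including the index gives 99.6 to 100%.

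**Equivalent sample loss.** Relative efficiency (the squared ratio of mean z with and without the index) is 1.03, 1.12, 1.31 and 1.58. The loss is 1 − 1/RE: 3%, 11%, 24% and 37%. Relative to an index measured with correlation 0.7 it is about 2%, 6%, 12% and 18%.

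**Day 14 risk difference.** The standardised estimate under (1) is the same with or without the index: 0.163, 0.158, 0.146 and 0.135. Its SE falls from 0.0465, 0.0467, 0.0471 and 0.0475 to 0.0462, 0.0456, 0.0443 and 0.0428.

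**Which strengths are plausible.** Suppose the episode ends when the last symptom clears, each symptom is present with probability 0.3 to 0.7, and durations within a patient correlate 0 to 0.8. The symptom count alone then has log hazard ratio 0.05 to 0.30 per SD. A 0–17 severity sum has 0.04 to 0.23 if severity does not affect duration, and 0.09 to 0.31 if each grade changes a graded symptom's duration by 28%. Days since onset is not in this calculation.

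**Type I error.** Null runs (10,000 per cell; strengths 0.3, 0.5, 0.7) gave 4.9–5.1% without the index, 4.8–5.1% with it, 5.1–5.4% with the correlation-0.7 version, and 4.8–5.1% with 10% of values filled by the pooled mean.

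**Second simulation.** Two independent covariates at 0.2, 0.35 and 0.5 each have combined strength √2 times that: 0.28, 0.49 and 0.71. At N = 400, Cox power was 98.0, 95.6 and 90.6% omitted and 98.8, 98.8 and 98.3% included, in line with the table. With no prognostic effect it was 98.9% both ways.

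**The case against.** Nothing here is an error. Four prespecified covariates are a legitimate choice, the synopsis and section 10.7.1 do not conflict, and the tests hold their level. The prognostic strength is assumed, and agreement between simulations confirms arithmetic rather than that premise. At strengths 0.15 and 0.3 the gain under the planned medians is 1 point or less, and section 10.1 already raised the sample from 232 to 400. The large losses need strengths of 0.5 to 0.7, which in turn need severity and days since onset to add a lot. Onset has no quantitative support here, and its direction is unknown. The required positive test within 72 hours of enrollment may narrow the spread of illness stage. The 0–17 score is unvalidated and need not beat a simple count. The day 14 risk difference could be reported with the four planned covariates alone. Finally, no separate SAP text is in the document, and it might add terms.

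All of this stands as a limit on size, and none of it removes the point. The enlarged sample was meant to cover unknown drop-out and other threats to power. Section 10.7.1 defers missing-data handling and the tipping-point analysis to the SAP but states the covariates as a settled list. The change uses data already collected.

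**Conclusion.** The point holds as an optional efficiency improvement. In the protocol as written, neither baseline symptom burden nor time since onset enters any planned model. Type I error is unaffected, and the 90% power target is not shown to be missed.

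At the better-supported strengths (0.15 to 0.3), omission costs 0.1 to 1.0 points of Cox power under the planned medians, equivalent to 3 to 11% of the sample. The cost rises to 7.8 points (98.5 − 90.7) at strength 0.7, but only about 1 to 2 points at any of the strengths tried (0.3 to 0.7) if the planned model itself estimates a hazard ratio near 1.58. It matters more if the true effect is smaller: at about 1.38 and strength 0.3, power is 86.0% against 89.8%. These sizes rest on assumed strengths and exponential times. Confidence is medium. The mismatch between the day 14 odds ratio and its estimand does not depend on prognostic strength.

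**What to change.** In the SAP, before unblinding:

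- Add two terms to the four planned covariates in the primary Cox model and in the day 7, 14 and 30 alleviation logistic models: a baseline symptom score (for example the four 0–3 items plus the count of the five present/absent items, range 0–17) and days from symptom onset to randomisation.
- State that these terms do not carry over to time to hospital admission or death, which section 10.7.2 ties to the primary method, or to the other hospitalisation, emergency-visit and mortality endpoints.
- Replace a missing baseline item or missing days since onset by the mean pooled across arms, so that every ITT patient stays in the model.
- Keep the Kaplan-Meier curves and medians as the marginal summary of the primary endpoint.
- With the day 14 logistic model, report a standardised risk difference with a confidence interval: predicted probabilities under each arm, averaged over all ITT patients.

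The cost is SAP wording, two model terms, one imputation rule and one extra output. No new data or visits are needed, and section 10 allows the change without a protocol amendment. The downsides are that the hazard and odds ratios become conditional on two more covariates, the simple score is not validated in the documents, and the gain may be 1 point or less under the plan's own effect.

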10.7.2 Secondary Efficacy Endpoints

The secondary efficacy endpoints of percentage of patients with hospital admission or death by day 30; all-cause mortality by day 30; COVID-19-related mortality by day 30; percentage of patients with subsequent emergency department visit or hospital admission for reasons attributable to COVID-19 by day 30; and percentage of patients with alleviation of COVID-19-related symptoms of cough, dyspnea, chills, feeling feverish, repeated shaking with chills, muscle pain, headache, sore throat, and new loss of taste or smell, defined as symptom-free for a continuous period of \geq 24 hours (ie, \geq 3 AM/PM assessments) by day 7, by day 14, and by day 30 will be analyzed using a logistic regression model. To improve the precisions on treatment effect estimation and inference, baseline covariate adjustments will be made for gender, age, race, and body mass index, as these are known COVID-19 risk factors. Analysis of the secondary efficacy endpoint of time to hospital admission or death will be performed using the same method as that used for the primary efficacy endpoint. The secondary efficacy endpoint of change from baseline in oxygen saturation levels will be summarized descriptively at all time points captured in the eDiary. The secondary efficacy endpoint of change from baseline in COVID-19 viral load in nasopharyngeal sample at day 30 will be summarized descriptively.

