The DMC will conduct a review of blinded safety data once 100 subjects have been enrolled. Details of the interim safety review will be described in detail in the DMC charter.

Sample Size and Power:

This study is designed to assess the efficacy and safety of ciclesonide MDI plus standard supportive care compared with placebo MDI plus standard supportive care. The primary endpoint is time to alleviation of COVID-19-related symptoms of cough, dyspnea, chills, feeling feverish, repeated shaking with chills, muscle pain, headache, sore throat, and new loss of taste or smell, defined as symptom-free for a continuous period of ≥ 24 hours (ie, ≥ 3 AM/PM assessments) by day 30. Assuming a median time to alleviation of 7 days for the ciclesonide arm and 11 days for the placebo arm (hazard ratio of approximately 1.58) with a total study duration of 30 days and a total of 201 events observed in the 2 arms combined, a sample size of approximately 232 patients (116 in each arm) is required to achieve 90% power at $\alpha = 0.05$ for the study. To account for an unknown drop-out rate in this patient population as well as other factors that may impact the overall power of the study, the planned sample size was increased to 400 patients (200 in each arm) for this study. Note that these are best estimates at this point as there is still much uncertainty regarding COVID-19.

TABLE OF CONTENTS

| D | escription | Page |
|---|---|------|
| 1 | Protocol Synopsis | 3 |
| 2 | List of Abbreviations and Definition of Terms | 11 |
| 3 | Introduction | 12 |
| | 3.1 Background Information on Coronavirus Disease 2019 (COVID-19) | 12 |
| | 3.2 Background Information on Ciclesonide and Rationale for Use in COVID-19 | 12 |
| | 3.3 Rationale for Dose Selection and Treatment Duration | 13 |
| | 3.4 Rationale for Subject Population | 14 |
| 4 | Study Objectives | 15 |
| | 4.1 Primary Objective | 15 |
| | 4.2 Secondary Objectives | 15 |
| | 4.3 Estimands | 16 |
| | 4.3.1 Primary Endpoint Estimand | 16 |
| | 4.3.2 Key Secondary Endpoint Estimand | 17 |
| 5 | Study Description | |
| | 5.1 Study Design | |
| | 5.2 Study Schedule | 19 |
| | 5.3 Study Visits and Procedures | 22 |
| | 5.3.1 Screening/Enrollment/Randomization Visit | 22 |
| | 5.3.2 Double-blind Treatment Period | 23 |
| | 5.3.3 Follow-up Period | |
| | 5.3.4 Early Termination Procedures | 24 |
| 6 | Patient Eligibility and Withdrawal Criteria | 25 |
| | 6.1 Number of Patients | 25 |
| | 6.2 Inclusion Criteria | 25 |

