10.3.2 Missing Data

All attempts will be made to minimize the amount of missing data. Sensitivity analyses may be conducted to evaluate the potential impact of the missing data.

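### Alleviation by day 14, 7 and 30 (steps 2 to 4 of the testing sequence): the planned logistic regression makes no use of partial follow-up from patients who leave the study still symptomatic

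*Combined protocol and SAP*

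**What the plan says.** Section 10.7.2 assigns the alleviation percentages a covariate-adjusted logistic regression: they "by day 7, by day 14, and by day 30 will be analyzed using a logistic regression model". Section 10.2 bases efficacy analyses on all randomized patients. In the fixed sequence of section 10.7.3, day 14, day 7 and day 30 are steps 2, 3 and 4, and a failure at any of them stops the later tests.

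Section 4.3.2 defines the day-14 estimand. Rescue medication, protocol violations and stopping study drug are disregarded, death and hospitalization are failures, and for ITT patients "all observed on-study data will be analyzed in accordance with the definition set forth above for intercurrent events". Withdrawal from the study and loss to follow-up are in neither group. Estimands for the other sequenced secondary endpoints, days 7 and 30 among them, are left to the SAP.

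On missing data, section 10.7.1 says "The SAP will describe how missing data will be handled in the primary analysis" and promises a tipping-point analysis, also for the primary endpoint. Section 10.3.2 adds only that "Sensitivity analyses may be conducted to evaluate the potential impact of the missing data". Section 6.4 allows withdrawal without replacement, and the early termination procedures in section 5.3.4 do not provide for continued symptom scoring. Section 10.1 expects attrition: 232 patients became 400 "To account for an unknown drop-out rate in this patient population" and for other factors.

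**The concern.** A patient who withdraws on day 6 still symptomatic has no day-14 or day-30 value. The primary Cox model can censor that patient on day 6. A logistic model for a yes/no outcome, as stated, has no place for six days of partial follow-up.

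Each simple way round this changes what is estimated. If the patient is excluded, inclusion depends on outcome: someone who alleviates on day 4 and leaves on day 6 stays in as a known success, while someone who leaves on day 6 unalleviated disappears. Rates are then too high even when dropout has nothing to do with symptoms. If the patient is counted as a failure, the rate becomes that of alleviating while still under observation, which is lower and falls further as dropout rises. When dropout differs between arms, either choice moves the comparison as well.

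The gap is limited to landmarks after departure. A patient who leaves unalleviated on day 20 is a known non-responder at days 7 and 14 and is unscored only at day 30.

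At stake are the key secondary endpoint and two further steps that must succeed before steps 5 to 11 can be tested.

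**Working it through.** **Inputs.** From section 10.1: medians of "approximately 7 days for the ciclesonide arm and approximately 11 days for the placebo arm", hazard ratio about 1.58, 30 days of follow-up, 200 per arm. Assumed: exponential recovery, and dropout independent of symptoms at a constant hazard. Dropout D by day 30 is not given, so a range is shown. Its top, 42%, is (400 − 232)/400. That is the whole inflation, which the plan shares with other factors, and is not a forecast.

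**The plan's own figure.** The plan says "For 90% power, approximately 201 events (recoveries) are required". Schoenfeld, two-sided 5%: 4 × (1.960 + 1.282)² / (ln 1.58)² = 42.03/0.2092 = 201. This reproduces. The plan gives no figure for the landmark percentages.

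**Formulas.** λ = ln 2/7 = 0.0990 (ciclesonide) or ln 2/11 = 0.0630 (placebo); δ = −ln(1 − D)/30. By day t:
- observed success S = λ/(λ+δ) × [1 − exp(−(λ+δ)t)]
- observed failure F = exp(−(λ+δ)t)
- unscored = 1 − S − F
- rate if excluded = S/(S+F); rate if failure = S; true rate = 1 − exp(−λt)

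**Example, day 30, D = 20% in both arms** (δ = 0.00744). Ciclesonide: F = 0.041, S = 0.892, unscored 0.067, excluded rate 0.892/0.933 = 0.956. Placebo: F = 0.121, S = 0.786, unscored 0.093, excluded rate 0.786/0.907 = 0.867.

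**Results** (%, ciclesonide/placebo; difference in points). True rates: day 14 75.0/58.6, difference 16.4; day 30 94.9/84.9, difference 10.0.

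| Day | Dropout by day 30 | Unscored | Excluded | Diff. | Failure | Diff. |
|---|---|---|---|---|---|---|
| 14 | 10/10 | 2.6/3.2 | 75.6/59.3 | 16.3 | 73.6/57.4 | 16.2 |
| 14 | 20/20 | 5.4/6.6 | 76.2/60.1 | 16.1 | 72.1/56.1 | 16.0 |
| 14 | 42/42 | 12.5/15.2 | 77.8/62.2 | 15.7 | 68.1/52.7 | 15.4 |
| 14 | 30/15 | 8.5/4.9 | 76.9/59.7 | 17.2 | 70.4/56.8 | 13.6 |
| 30 | 20/20 | 6.7/9.3 | 95.6/86.7 | 8.9 | 89.2/78.6 | 10.6 |
| 30 | 42/42 | 15.0/20.4 | 96.5/89.0 | 7.5 | 82.0/70.8 | 11.2 |
| 30 | 30/15 | 10.3/6.9 | 96.0/86.2 | 9.8 | 86.1/80.3 | 5.8 |

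**Power of the day-30 comparison on its own.** Φ(difference/SE − 1.960), with unpooled SE = √(p₁q₁/n₁ + p₂q₂/n₂).
- No dropout: 9.97/2.97, giving 92%.
- Equal 20%, excluded (n about 187 and 181): 8.92/2.94, giving 86%.
- Equal 20%, failure: 10.56/3.64, giving 83%.
- 30% against 15%, failure: 5.81/3.73, giving 34%.

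**Kaplan-Meier landmark.** With the large-sample Greenwood variance per arm, exp(−2λt) × λ/(λ+δ) × [exp((λ+δ)t) − 1]/200, the target stays at 10.0 points. At equal 20% the SE is 3.21 and power 9.97/3.21 − 1.960 = 1.15, about 87%. At 30% against 15% the SE is again 3.21, so power is also about 87%. At day 14 with equal 20% the SE is 4.8, against 4.6 with no dropout.

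**The case against.** **Size.** At the key endpoint the effect is modest. With equal dropout, even at 42%, the day-14 difference moves by 1 point or less against an SE of about 4.6. Larger shifts need day 30 or unequal dropout, and nothing in the protocol predicts an imbalance. This stands. Much of the power loss at equal dropout is also lost information that no method recovers: at 20% the landmark estimate gives about 87%, against 86% and 83%.

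**Type I error.** A reader might infer that unequal dropout pushes false positives above 5%. The documents do not support that. A stand-alone day-30 test under no effect, with 30% against 15% loss and failure scoring, does reject in about 23% of trials, nearly all favouring placebo. But section 10.7.3 lets these tests run only after the primary test succeeds. In 20,000 simulated null trials with that imbalance (both medians 11 days, log-rank standing in for the Cox test), step 1 rejected in 5.2%, the sequence passed day 14 in 2.3% to 2.4%, and it passed day 30 in 0.4% (excluded) or 0.7% (failure).

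**Forced choice.** A reader might also infer that logistic regression must either exclude these patients or fail them. It need not: multiple imputation or inverse-probability weighting fits the same model. The plan names neither. Exclusion would also conflict with the ITT set of all randomized patients, so it cannot be called the plan's literal instruction.

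**Failure scoring as a choice.** Counting non-completion as non-response is a recognised composite approach, and section 4.3.2 takes it for death and hospitalization. It is defensible if declared, but section 4.3.2 does not declare it for withdrawal.

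**The SAP.** Section 10 sends detail to an SAP whose text is not in the file, and the day-7 and day-30 estimands are deferred there. That could close part of the gap. The day-14 estimand, however, is set out in the protocol, and the missing-data deferral names only the primary analysis.

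**Conclusion.** The concern holds as a weakness in the stated method for steps 2 to 4: it does not use partial follow-up, and withdrawal or loss before a landmark has no stated score. Under independent dropout of 10% to 42% by day 30, equal by arm, day-14 rates are off by about 1 to 7 points and the day-14 difference by 1 point or less.

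The main exposure is day 30. The 10.0-point difference becomes 8.9 or 10.6 at equal 20% dropout, with power down from about 92% to 86% or 83%, and 5.8 under failure scoring with 30% loss on ciclesonide and 15% on placebo. The direction depends on which arm loses more. With 10% loss on ciclesonide and 20% on placebo, failure scoring gives 13.5 points, which favours the drug.

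These sizes rest on exponential recovery and assumed dropout rates. Symptom-related dropout could make them larger, and the documents give nothing to bound that. The change is worth making because it is cheap and gives an estimate that does not depend on the amount of non-informative dropout. No inflation of overall Type I error is claimed.

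**What to change.** In section 10.7.2, or in the SAP, derive steps 2 to 4 from the same censored time-to-alleviation data as the primary endpoint:
- Compare the probability of alleviation by day 14, 7 and 30 as a difference of Kaplan-Meier landmark estimates. This matches the difference in response probabilities named in section 4.3.2. To keep the planned covariates, use pseudo-value regression or regression weighted by the inverse probability of remaining uncensored.
- Censor patients who withdraw or are lost before alleviation at their last eDiary entry.
- Keep deaths and hospitalizations as failures under section 4.3.2, carried as not alleviated to day 30 rather than censored at the event. State the same rule for days 7 and 30.
- Extend the tipping-point analysis of section 10.7.1 to the day-14 endpoint.

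The cost is SAP wording and modest programming, with no new data or patients. Section 10 allows changes in statistical methods before unblinding to be documented in the SAP without a protocol amendment. The downsides are slightly wider intervals than with complete data (day-14 SE about 4.8 against 4.6 points at 20% dropout) and reliance on non-informative dropout, which the extended tipping-point analysis would test.
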